## 1. Background

Diabetes Mellitus represents a growing health challenge in UK with an estimated prevalence of 2.9 million representing 4.45% of the population. This is expected to soar to 5 million by 2025 in UK. The scale of the problem is similar globally with an estimated prevalence of 366 million that is expected to rise to 552 million by 2030. (1, 2)

Diabetes is associated with an increased risk of morbidity and mortality especially if poorly controlled. With increasing prevalence, health authorities in UK and worldwide are facing increasing challenges to deal with the burden of diabetes and its complications. It is currently estimated that 10% of NHS budget is spent on diabetes.(1)

Intensive treatment of diabetes and good glycaemic control has been shown to reduce the risk of complications (2, 3). A core component in a successful diabetes management strategy, particularly in subjects who are insulin treated, is glucose monitoring. It enables subjects to intensify insulin therapy with a subsequent reduction in diabetes-related complications while minimizing the risk of hypoglycaemia. There is evidence of improvement in glycaemic control associated with increased frequency of self-monitoring of blood glucose (SMBG) or with the use of continuous glucose monitoring (CGM) (4-6). Recent studies showed that the use of CGM is associated with reduced time spent in hypoglycaemia and reduction in HBA1c level in children and adults with type 1 diabetes with benefits seen even in those with HBA1c values at target (7, 8).

Since 1971, when the first glucose monitor was used, the most common method of glucose monitoring remains the use of intermittent capillary blood glucose sensors using standard finger-prick methods. This method does not provide the user with information about duration, direction and magnitude of glucose change over time. Furthermore, it is uncomfortable and painful which can result in poor compliance with the recommended frequency of glucose monitoring with subsequent negative impact on diabetes control. Many alternative monitoring methods have been investigated to allow continuous glucose monitoring (CGM). Continuous glucose monitoring devices that have gained approval for marketing depend on amperometric electro-chemical technology using Glucose Oxidase enzyme (GOx) for detection of the interstitial fluid glucose. This has been coupled with either microdialysis or reverse iontophoresis methods for glucose extraction. However, currently the most commonly used CGM devices in clinical practice depend on an electro-chemical glucose sensor in the form of a needle that penetrates the skin with the sensor tip in the subcutaneous tissue. As these sensors use interstitial fluid (ISF) as the diagnostic fluid, they require calibration to capillary blood glucose as the ISF glucose concentration is approximately 60% of that in blood and changes in ISF glucose lag 6-7 minutes behind changes in blood (9). Despite their clinical benefits, they remain invasive, painful, costly and inaccurate, particularly in the hypoglycaemic range (10). They also require regular calibration against blood glucose values as they are susceptible to signal drift as a result of surface deposition of proteins and cells which is followed by connective tissue encapsulation (biofouling) affecting sensor's accuracy and life span (11). To overcome

these problems, emerging CGM technologies attempt to minimize the level of invasiveness without compromising on sensor accuracy or lifespan.

Human skin comprises the epidermis, dermis and subcutaneous tissue. The outer 10-15  $\mu\text{m}$  of epidermis, called stratum corneum, is primarily made of dead tissue and is responsible for skin barrier characteristics. The viable epidermis, up to 50-100  $\mu\text{m}$  below the stratum corneum, contains living cells, but is devoid of blood vessels and contains few nerves. Below the viable epidermis lies the dermis, 800 – 1500  $\mu\text{m}$  in thickness, which contains nerves and blood vessels at approximately 400  $\mu\text{m}$  depth from skin surface (12).

In order to allow minimally invasive access to ISF for CGM, research in microprobe array technology has developed in recent years. The idea of microprobe use was first suggested in 1976 by Gestel and Place to penetrate the stratum corneum layer for drug delivery. Thanks to advances in microfabrication in 1990s, manufacturing of microprobes is made possible. Since then, research in microprobe array technology has developed to explore different applications using microprobe arrays of different geometries manufactured from a range of materials including polymers, metals, glass or silicon. This novel technology provides a minimally invasive alternative to the conventional use of needles or lancets. It can be employed for therapeutic purposes by allowing or enhancing transdermal drug delivery. It can also be used diagnostically by allowing access to biofluids (ISF or blood) which can be used for analysis of physiologically relevant analytes (e.g., glucose or lactic acid). An array containing several microprobes is used to penetrate the stratum corneum. This can access ISF without impinging on the dermal nerves fibers or blood vessels. It also provides a large surface area for the enzymatic electro-chemical reaction to sense ISF glucose, potentially resulting in improved accuracy of glucose sensing, even in the hypoglycaemic range. Therefore, this new technology provides the potential for accurate continuous glucose monitoring in a less painful minimally invasive way. However, for this technology to be included into mainstream clinical medicine, microprobe arrays have to fulfill the requirements of low cost, mass production, mechanically robust design, bio-compatibility and accuracy.

Over the last ten years, several groups have been working on the development of this technology aiming to design microprobe arrays that fulfill these requirements and can be used for analysis of body fluids or drug delivery.

The mechanics of microprobe insertion into the skin is of paramount importance to device performance and safety. Successful insertion depends on microprobe geometry and material. It also depends on skin resistance to penetration. All these factors determine the force needed for insertion and risk of fracture of microprobes. Microprobes need to be of the correct geometry and physical properties to allow for a small insertion force. If the force required for insertion exceeds fracture force, needles will break or bend before insertion occurs. Several studies investigated microprobe mechanics and have demonstrated that effective microprobe insertion is achieved by a small tip radius and sufficient length to overcome skin resistance, while mechanical strength is increased with increasing wall thickness, needle base diameter and Young's modulus (measure of stiffness of material). By minimizing force of insertion and maximizing

fracture force, a large safety margin can be achieved allowing for successful skin insertion without mechanical failure (13-15).

To assess device safety, several studies were conducted to assess pain, skin irritation, skin damage, bleeding and risk of infection associated with microprobe application with comparison to hypodermic needles or conventional lancets. With the minimally-invasive nature of the device, The studies show that microprobe application provides many advantages over conventional needles and lancets including: less or no pain (16, 17), no bleeding, reduced risk of infection (18), minimal tissue trauma (17, 19), minimal skin irritation (19, 20) and rapid skin recovery (17, 19, 21). Various techniques have been employed to assess microprobe penetration to skin layers. Light microscopy or colored dye application following microprobe removal allow for *en face* visualization of the penetrated skin. Measurement of transepidermal water loss (TEWL) can also be used to confirm skin penetration. None of those techniques provide information on the depth of the created microchannels. To do so requires biopsy of the microprobe treated area and histological examination. Recent research has employed confocal microscopy and optical coherence tomography imaging techniques as an alternative to histological examination.

The use of microprobe arrays in ISF extraction for glucose monitoring has been successfully demonstrated (22). Hollow microneedles manufactured of glass (700-1500  $\mu\text{m}$  in length, 15-40  $\mu\text{m}$  tip radii) were used to penetrate the skin of 15 rats and 6 human subjects before applying a vacuum to extract ISF and measure glucose concentration. Skin at the insertion site was examined by bright field microscopy and multiphoton confocal microscopy. Skin histology was also examined using bright field microscopy. This confirmed skin penetration and showed similar geometry between the created hole and that of the microprobe. Analysis of extracted ISF glucose showed good correlation to capillary blood glucose with a lag time of less than 20 minutes following an insulin injection.

The Institute of Bio-medical Engineering department at Imperial College has adapted and improved the existing methodology to manufacture a novel continuous sensor platform using microprobe arrays and classical enzyme electrochemistry in order to overcome difficulties related to bio-incompatibility, biofouling, clogging and local variations in temperature, sweat and vascularity.

## **2. The Imperial College microprobe array continuous glucose sensor:**

[figure not shown]
### **2.1- Device description:**

The Imperial College microprobe array continuous glucose sensor consists of a three dimensional out-of-plane microprobe arrays, with 36 - 64 microprobes perpendicular to the base plate and arranged as 6x6 or 8x8 arrays. The microprobes are 800-1000 $\mu\text{m}$  in length with a base of 500-600 $\mu\text{m}$  and tip diameter of 10-50 $\mu\text{m}$ . The microprobe arrays are made of SU-8, an epoxy material, metallised with platinum and are functionalized with glucose oxidase (GOx) (EC 1.1.3.4) incorporated in electropolymerised polyphenols layer. The electropolymerised polyphenols layer serves also as an outer coating membrane to prolong

the linear working range (from 0 to 30mM of substrate) and increase resistance to interfering agents such as dopamine, ascorbic acid, acetaminophen, or uric acid (23).

This device is gently pushed into the skin surface using an applicator, which allows it to penetrate through the skin layers and access the interstitial fluid in a minimally invasive manner.

The materials that the device brings in contact with the layers of skin are polyphenols, platinum coating, the glucose oxidase based enzymatic system and in case of damage to the probes the underlying SU-8 epoxy layer. SU-8 is a high contrast, epoxy-based photoresist designed for micromachining and other microelectronic applications, where a thick chemically and thermally stable image is desired. The SU-8 epoxy used for research studies has viscosity of 12250cSt. A literature review on SU-8 epoxy based devices has demonstrated that SU-8 epoxy and platinum based drug delivery devices are biocompatible and showed reduced biofouling (24). Glucose oxidase and platinum are routinely used in other commercially available CE-marked predicate devices (Enlite sensor, Medtronic. Freestyle Navigator, Abbott Diabetes Care. Dexcom Seven, Dexcom). Polyphenols are natural products and are listed as inactive ingredients for approved drugs products on the FDA (25).

Figures 1 showing scanning electron microscopy image of the Imperial College microprobe array continuous glucose sensor.

[figure not shown]

Figure 2 showing schematic of the microprobe array sensor

## 2.2- Fabrication process:

This involves the use of an aluminium metal master, which is used to create moulds of Polydimethoxy Siloxane (PDMS).

The master is fabricated using an Electrical Discharge Machining (EDM) technique. EDM is a controlled metal-removal process that is used to remove metal by means of electric spark erosion. The metal-removal process is performed by applying a pulsating electrical charge of high-frequency current through the electrode to the work piece. This erodes very tiny pieces of metal from the work piece at a controlled rate.

The moulds are casted with the commercially available epoxy material SU8 50 using both spinning or using vacuum. Once the epoxy is filled into the microcavities of the mould they are cross-linked by exposure to UV light at 254 nm for 30-60 minutes. The samples are cooled down at 4°C and the PDMS layer is peeled off to obtain the cross-linked epoxy microprobe arrays.

An alternative to SU-8 is Injection molding of polycarbonate. For the injection molding of polycarbonate, a metal mold of aluminium is prepared using CuW microelectrodes. An injection molding setup is used to introduce molten polycarbonate at high pressure, once the polycarbonates is cooled it solidifies into bare device. Polycarbonate is a biocompatible material and is one of most commonly used and most widely tested in the medical device industry.

The bare devices are masked and sputtered with metal to obtain the working and reference electrodes. For working electrode, a platinum target is used to sputter 50 nm of Pt whilst for the reference electrode a silver target is used to sputter 100 nm of Ag.. The metallised devices are functionalised by electropolymerisation of a 50 mM of phenol solution consisting of 10 mg/mL glucose oxidase (GOx) enzyme. Electropolymerisation is done by biasing the working electrodes against a Ag/AgCl reference electrode at 0.9 V for 15 minutes.

[figure not shown]

Figure 3 showing fabrication process.

### **3. Validation process:**

#### **3.1-Functional Validation (in vitro):**

The devices were tested using a chronoamperometric technique by subjecting the functionalised devices to varying concentrations of glucose ranging from 0 - 30 mM. Microprobe array glucose sensors reproducibly responded to changing glucose concentrations with linear responses seen in the physiological range. Currents measured were over one hundred times higher compared to those measured using the subcutaneously implanted disc electrode that is currently used in clinical practice for

CGM. This results in improvement of signal:noise ratio and thus improving accuracy and reproducibility (26).

Apart from the potential for this new technology to provide a painless accurate method for continuous sensing of ISF glucose concentration, it is also possible to partition the microprobe arrays and immobilize different enzymes across multiple sensing areas sharing a common reference electrode for continuous multi-analyte sensing. Partition may also allow multiple sensors in a voting or averaging system for the same analyte, therefore improving sensor performance.

[figure not shown]

Fig. 4: Chronoamperometric measurements obtained for varying glucose concentration..

### 3.2. Mechanical Validation (in vitro and ex vivo):

Aim of mechanical validation study is to assess the ability of the device to penetrate stratum corneum, to access interstitial fluid and analyse its glucose content, without fracture of microprobes ex vivo through insertion tests and to assess device's mechanical robustness in vitro through fracture tests.

#### 3.2.1. Insertion tests:

Human skin samples were obtained from plastic surgery at Charing Cross Hospital – Imperial College Healthcare NHS Trust after approval from Imperial College Human Tissue Bank (ICHTB) and patients' consent. ICHTB is approved by NRES to give “deemed ethics” for research projects that use extra samples of anonymised tissue and fluids collected specifically for research. Using Instron force-displacement test station, microprobe arrays were applied to skin surface using forces of 7, 10, 15, 20 and 25 Newton at a speed of 3 mm/s. Once reached, target force was maintained for duration of 60 seconds. Following removal of the device, methylene blue dye was applied to the microprobe array-

treated skin area for 20 minutes before it was carefully wiped using alcohol swap. Skin was then examined under digital microscopy to identify created micropores. Skin was also examined histologically to confirm penetration and assess penetration depth. Results have demonstrated the ability of microprobes to penetrate stratum corneum using forces as low as 7 Newton. Insertion ratio (number of created micropores divided by number of microprobes) was proportional to force used. Using force of 20N or above resulted in insertion ratio of almost 100%. Scanning electron microscopy examination of microprobe arrays following insertion tests showed structural integrity of the device.

[figure not shown]

Figure 5: Digital microscopy image of a microprobe array treated human skin (*ex vivo*) following application of methylene blue dye to confirm successful penetration. This shows extravasation of the dye in deeper skin layer after penetration of stratum corneum layer.

[figure not shown]

Figure 6 showing penetration of stratum corneum (arrow) with microchannels (penetration depth of 300 microns) created by microprobes.

[figure not shown]

Figure 7 showing scanning electron microscopy image of microprobe array following successful skin penetration using force of 20 Newton. This shows intact integrity of the device following successful skin penetration.

### 3.2.1. Fracture tests:

Using Instron force-displacement test station, microprobe arrays were pressed against a metal probe using forces of 50, 100, 200, 300 and 400 Newton. Using forces up to 200 Newton only resulted in slight bending of microprobes' tips. Microprobe height reduction was observed when forces higher than 300 Newton were used. Even with the use of a force of 400N, there was no evidence of breakage of microprobes or base plate. This implies a high safety margin of the device from the mechanical aspect.

[figure not shown]

Figure 8 showing scanning electron microscopy image of a microprobe array after applying force of 400 Newton. Use of such a large force only resulted in bending of microprobes and height reduction without any fractures or collapse of the microprobes.

#### 4. Trial Objectives and Purpose

This trial assesses the safety and efficacy of the Imperial Microprobe array biosensor for continuous monitoring of ISF glucose.

Safety will be assessed in relation to skin inflammation, skin damage, risk of fracture of microprobe tips within skin layers and pain. This will be assessed over six hours initially then over 24 hours in non-diabetic volunteers then over 24 hours in subjects with type 1 diabetes as in-patients and finally, in ambulatory situation over 5 days.

Efficacy will be assessed mechanically (ability to penetrate stratum corneum) and functionally (ability to sense ISF analytes). Functional efficacy of microprobe arrays to continuously monitor ISF glucose will be assessed in comparison to venous blood glucose levels and ISF glucose using iPro2 in as inpatients (phase3) then in an ambulatory state (phase 4).

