**Visit:**

- Attend the Wellcome Trust-Sir John McMichael Clinical Research Facility at the Hammersmith Hospital campus of Imperial College between 9:00 - 10:00 am. Female subjects of childbearing age will have a urine pregnancy test performed.
- The outer margin of a 2 cm^2 skin area on the ventral aspect of the non-dominant forearm will be marked before the application of sterile microprobe array to the center of this skin area. The marked skin area will be shaved if hairy. Microprobe insertion will be achieved by applying gentle pressure. Microprobe array will be secured in place with an adhesive plaster for six hours with 5 minutes sampling as moving average of 1 minute intervals.
- An 18-G intravenous cannula will be inserted in the non-dominant upper limb for venous sampling. Throughout the 6 hours, 2.5mL venous blood will be taken at 15 minutes interval and will be distributed for venous glucose estimation using YSI analyser. Maximum blood volume collected over study visit duration is 60mL.
- Six hours after microprobe insertion (at 16:00), the microprobe array and intravenous cannula will be removed.
- Skin area around the microprobe array will be inspected at 1, 2 hours post-insertion and after device removal by a doctor for any evidence of skin inflammation using a 4-point scale (none, mild, moderate and severe).
- Following removal of the device, the microprobe treated skin area will be examined using confocal microscopy imaging technique to confirm penetration and examine the created microchannels.
- Microprobe arrays will be examined for integrity before and after application using scanning electron microscopy (SEM).
- Visual analogue scale (VAS) will be used to assess pain resulting from microprobe insertion in comparison with pain resulting from blood sampling.

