- Skin area around the microprobe array will be inspected at 1, 2, 6 hours post-insertion and after removal of the device at 24 hours by a doctor for any evidence of skin inflammation using a 4-point scale (none, mild, moderate and severe). This will be compared to skin area around iPro2 sensor insertion site.
- Following removal of the device at 24 hours, the microprobe treated skin area will be examined using confocal microscopy imaging technique to confirm penetration and examine the created microchannels.
- Microprobe arrays will be examined for integrity before and after application using SEM.
- Visual analogue scale (VAS) will be used to assess pain resulting from microprobe insertion in comparison with pain resulting from blood sampling and pain resulting from insertion of iPro2 sensor.
- At the end of the 24 hour period, subjects will be asked to fill a validated acceptability questionnaire.

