#### **Visit:**

- On the morning of the visit, subjects will be instructed to have their standard breakfast and to adhere to their usual practice of diabetes management; this will be maintained throughout the study period.
- Attend the Wellcome Trust-Sir John McMichael Clinical Research Facility at the Hammersmith Hospital campus of Imperial College between 9:00 - 10:00 am
- Between 10:00 – 11:00, microprobe array and iPro2 device will be implanted in each subject.
- The outer margin of a 2 cm^2 skin area on the ventral aspect of the non-dominant forearm will be marked before the application of sterile microprobe array to the center of this skin area. The marked skin area will be shaved if hairy. Microprobe insertion will be achieved by applying gentle pressure. Microprobe array will be secured in place using adhesive plaster for 24 hours with 5 minutes sampling as moving average of 1 minute intervals.

- Medtronic iPro2 (Northridge, California) retrospective/blinded continuous glucose monitoring sensor will be implanted in the anterior abdominal wall and calibrated as per manufacturer's instructions.
- Subjects will be allowed to go home with advice to have normal daily activity with no alteration to their insulin doses or other aspects of diabetes management. Subjects will be asked to keep a food diary and a diary for self-monitored blood glucose levels.
- Subjects will attend the research unit on day 6 between 9:00-10:00. The 2 devices will be removed. Skin area around the microprobe array will be inspected by a doctor for any evidence of skin inflammation using a 4-point scale (none, mild, moderate and severe). This will be compared to skin area around iPro2 sensor insertion site.
- Following removal of the device, the microprobe treated skin area will be examined using confocal microscopy imaging technique to confirm penetration and examine the created microchannels.
- Microprobe arrays will be examined for integrity before and after application using SEM.
- Visual analogue scale (VAS) will be used to assess pain resulting from microprobe insertion in comparison with pain resulting from blood sampling and pain resulting from insertion of iPro2 sensor.
- At the end of the 5 days ambulatory period, subjects will be asked to fill a validated acceptability questionnaire.

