## 7. Timescale

It is anticipated that the studies will take place over 4 years. Non-diabetic subjects will be recruited to the study for phase 1 and 2 (2 visits). Subject with type 1 diabetes will be recruited for phases 3 and 4 of the study for up to 12 - 18 months, with a total of 2 visits in that timeframe.

**8. Potential risks and benefits** The potential risks and burdens for research participants are as follows:

Skin inflammation may occur with the use of microprobe arrays. A literature review shows this to be minimal and transient. Subjects will be examined regularly by a doctor to assess the degree of any inflammatory reaction and the need for any intervention (ending the study or the use of local/systemic therapy if required).

Pain may result from microprobe array insertion. A literature review shows this to be absent or very minimal when compared to traditional needles or lancets. The array will be inserted with gentle manual pressure and pain score will be assessed in phases 2, 3 and 4.

In all visits (excluding phase 4) there is either a venous blood test or insertion of an intravenous cannula. These have the potential to cause discomfort. This will be minimised by experienced research personnel performing the procedure and appropriate use of equipment and aseptic technique.

In phases 3 and 4, subjects will have a continuous glucose-monitoring sensor (iPro2, Medtronic) inserted in anterior abdominal wall subcutaneous tissue. Sensor insertion can be associated with some discomfort but the insertion devices are spring-loaded with introducers, making the process rapid and often painless. Any discomfort will be minimised by adhering to manufacturer's instructions.

Assessment of efficacy of the device will be in comparison to venous glucose levels and a commercially available continuous glucose sensor over a period of twenty-four hours as in-patients. 2.5 mL venous blood will be taken at 30 minutes intervals apart from the period between 11:00 - 22:00 when the blood will be taken hourly.

During studies involving subjects with type 1 diabetes, subjects will adhere to their usual practice of diabetes management.

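### Pain is a safety objective over 6 hours, 24 hours and 5 days of wear, but the pain score in all four phases is defined only for insertion

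*Protocol*

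**What the plan says.** Section 4 (Trial Objectives and Purpose) names four safety domains: "Safety will be assessed in relation to skin inflammation, skin damage, risk of fracture of microprobe tips within skin layers and pain". The next sentence gives the time span: "This will be assessed over six hours initially then over 24 hours in non-diabetic volunteers then over 24 hours in subjects with type 1 diabetes" and "finally, in ambulatory situation over 5 days". Section 5 lists a pain score as a secondary outcome in each of the four phases.

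The measurement is set in the visit descriptions. For Phases 1 and 2: "Visual analogue scale (VAS) will be used to assess pain resulting from microprobe insertion in comparison with pain resulting from blood sampling". For Phases 3 and 4 the iPro2 sensor is added as a comparator, and the VAS is to "assess pain resulting from microprobe insertion in comparison with pain resulting from blood sampling and pain resulting from insertion of iPro2 sensor". None of the four descriptions gives a time for the VAS.

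Section 8 (Potential risks and benefits) presents pain as a consequence of array insertion and says that "pain score will be assessed in phases 2, 3 and 4".

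**The concern.** The safety programme is built on increasing wear time, and Section 4 places pain among the domains followed over that time. A rating tied to insertion describes one event at the start of each phase. It cannot show whether the site becomes sore while the array is worn, or whether removal hurts.

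This matters because the background criticises existing worn sensors as painful and presents the microprobe array as a less painful, potentially painless, way to monitor continuously. That claim covers wear as well as insertion. If the plan is followed exactly, the 5-day phase could be reported as showing little pain although only insertion was rated. Ratings that were never collected cannot be recovered by any later analysis plan, so this is a matter for the protocol.

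**Working it through.** No formula applies, and the protocol states no figure on this point to reproduce. The check sets the objective beside the measurement in each phase (Section 4 for the span, the Section 5 visit descriptions for the rest).

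| Phase | Span in Section 4 | What the VAS rates | VAS comparator | Skin inspection times | Pain rating during wear or at removal |
|---|---|---|---|---|---|
| 1 | 6 h | insertion | blood sampling | 1 h, 2 h, after removal | none specified |
| 2 | 24 h | insertion | blood sampling | 1 h, 2 h, 6 h, after removal | none specified |
| 3 | 24 h | insertion | blood sampling, iPro2 insertion | 1 h, 2 h, 6 h, after removal at 24 h | none specified |
| 4 | 5 days | insertion | blood sampling, iPro2 insertion | at removal on day 6 | none specified |

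1. **Count.** The VAS is defined as insertion pain in 4 of 4 phases. A pain rating during wear or at removal is specified in 0 of 4.
2. **What changes between phases.** The array goes in by the same stated means each time, gentle pressure. Phases 3 and 4 change the population (type 1 diabetes) and add the iPro2 comparator. Wear time also changes, but it comes after the event being rated, so it cannot affect what the pain score measures.
3. **Contrast with skin inflammation.** That domain has inspections spread over wear in Phases 1 to 3 and one at removal in every phase. The protocol therefore sets assessment times where it means to follow something over wear. It sets none for pain.
4. **Other sources.** Phases 3 and 4 end with an acceptability questionnaire whose content is not described. Phases 1 and 2 have none. Section 9 calls for full recording of adverse events, without a pain scale.
5. **Phase 1 scoring.** Section 8 names phases 2, 3 and 4 for pain scoring. Section 5 lists a pain score among the Phase 1 outcomes and includes the VAS in the Phase 1 visit.
6. **Phase 4 comparator.** The Phase 4 VAS compares with blood-sampling pain. The Phase 4 visit lists no blood sampling by the study team, and Section 8 excludes Phase 4 from the visits with a venous test or cannula. Subjects do keep a diary of self-monitored glucose. If finger-prick pain is the intended comparator, the text does not say so.

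**The case against.** The strongest reply is that Section 4 sets the time span for safety as a whole and does not promise repeated ratings of every domain. Tip fracture stands in the same sentence and is checked only by electron microscopy before and after use. Section 8 treats pain as an insertion risk, the background compares the device with needles and lancets, and the VAS comparators fit that narrower question. On this view the mismatch is one of wording, and a clause limiting the pain objective to insertion would repair it.

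Part of this stands. Limiting the objective is a legitimate second-best repair, and pain is a secondary outcome throughout. But the tip-fracture parallel does not rescue the pain score: an array examined after removal has been through the whole wear period, whereas an insertion rating has not.

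Three stronger readings are tempting, and the document does not support them:

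- **Recall.** The VAS item comes after the removal item in each visit list, so a reader might infer that insertion pain is recalled 6 hours, 24 hours or 5 days later. The lists are not chronological. In Phase 1 the 1-hour and 2-hour inspections also follow the removal item. The VAS time is simply unstated.
- **No added value.** A reader might infer that the later phases add nothing on pain. They add insertion pain in a new population and against a second device. What they lack is information on wear.
- **Subjects wrongly called pain free.** Soreness on day 4 with no insertion pain would leave the pain score at zero, but the questionnaire or adverse event records might still capture it. The protocol gives no rate of wear or removal pain, so the number of subjects affected cannot be estimated.

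**Conclusion.** The mismatch is real and can be seen directly in the text. The objective covers pain over 6 hours, 24 hours and 5 days, and the pain score covers insertion only, in all four phases. The conclusion is firm for the pain score as defined. It rests on the VAS being the only pain instrument, which is so as far as the protocol describes its instruments. The questionnaire and adverse event records may hold something on wear discomfort, but since neither is described as a pain measure they do not close the gap.

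The size is best given as 0 of 4 phases with a wear or removal rating. A count of unrated hours in Phase 4 would be unsafe, because that visit text has the array secured for 24 hours while the phase is described as lasting 5 days; those statements also need to be reconciled.

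This should be corrected before data collection. It does not threaten any primary outcome. The Phase 1 scoring conflict and the Phase 4 comparator conflict are smaller but clear.

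**What to change.** Preferred change:

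- State that the insertion VAS is taken at insertion.
- Add a VAS for pain at the array site at each skin inspection already scheduled during wear (1 and 2 hours in Phase 1; 1, 2 and 6 hours in Phases 2 and 3), and at device removal in every phase.
- In Phase 4, add one daily site-pain line to the diary that subjects already keep.
- Report insertion, wear and removal pain separately.

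This adds three short ratings in Phase 1 (1 h, 2 h, removal), four in Phases 2 and 3 (1 h, 2 h, 6 h, removal), and one removal rating plus a daily diary line in Phase 4. No extra visit is needed. The downside is slight subject burden.

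If this is not wanted, limit the pain objective in Section 4, and any conclusion about pain, to insertion.

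In either case, reconcile Section 8 with the Phase 1 outcomes and visit on whether pain is scored in Phase 1. Also state what the blood-sampling comparator in Phase 4 refers to, or remove it. These two changes cost only a text correction.
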